**Novo Nordisk**

## PASS information

Title	A multinational, prospective, open labelled, non-controlled, non-interventional post-authorisation study of turoctocog alfa pegol (N8-GP) during long-term routine prophylaxis and treatment of bleeding episodes in patients with haemophilia A
Protocol version identifier	Version 2.0, 17 April 2020
Date of last version of protocol	N/A
EU PAS Register number	Study not yet registered
Active substance	Turoctocog alfa pegol (N8-GP) ATC code: XXXXXXXXXX
Medicinal product	Esperoct ®
Product reference	
Procedure number	
Marketing authorisation holder(s)	Novo Nordisk A/S [name]
Joint Post Authorisation Safety Study (PASS)	No
Research question and objectives	This study is designed for the purpose of obtaining safety information from real-world post authorisation use.

Protocol  
NN7088-4029  
UTN: U1111-1235-6007  
EU PAS No.

~~CONFIDENTIAL~~

Date:  
Version:  
Status:  
Page:

17 April 2020  
2.0  
Final  
3 of 49

**Novo Nordisk**

#### Primary objective:

to investigate the long-term safety of N8-GP including the PEG moiety of the substance during routine prophylaxis in patients with haemophilia A.

[figure not shown]
#### Secondary objective:

to further evaluate the general safety of N8-GP during routine use in patients with haemophilia A under the circumstances in which it was prescribed by the physician. This will include FVIII inhibitors and allergic/hypersensitivity reactions.

#### Countries of study

Expected countries: Germany, Spain, Italy, Switzerland, Slovenia, Slovakia, Croatia, Portugal, Greece  
The list of countries is not complete

**Novo Nordisk**

## 2 List of abbreviations

AE	Adverse Event
AESI	Adverse Event of Special Interest
ALT	Alanine aminotransferase
AR	Adverse Reaction
CRF	Case Report Form
CRO	Contract Research Organisation
CV	Curriculum Vitae
eCRF	Electronic Case Report Form
EDC	Electronic Data Capture
eGRF	Estimated Glomerular Filtration Rate
EMA	European Medicines Agency
ENCePP	European Network of Centres for Pharmacoepidemiology and Pharmacovigilance
EU PAS	The EU electronic register of post-authorisation studies maintained by the European Medicines Agency
FDA	Food and Drug Administration
FPFV	First Patient First Visit
FVIII	Factor VIII
GPP	Good Pharmacoepidemiological Practice
GVP	Good Pharmacovigilance Practice

Protocol  
NN7088-4029  
UTN: U1111-1235-6007  
EU PAS No.

~~CONFIDENTIAL~~

Date:  
Version:  
Status:  
Page:

17 April 2020  
2.0  
Final  
9 of 49

**Novo Nordisk**

ICH-GCP	International Conference on Harmonisation/GCP
IEC	Independent Ethics Committee
IRB	Institutional Review Board
ITI	Immune Tolerance Induction
LAR	Legally Acceptable Representative
LPLV	Last Patient Last Visit
MAH	Marketing Authorisation Holder
N8-GP	Turoctocog alfa pegol
NIS	Non-interventional Study
PASS	Post Authorisation Safety Study
PEG	40 kDa glycoPEGylated
PK	Pharmacokinetics
PTPs	Previously treated patients
rFVIII	Recombinant factor VIII
SAE	Serious Adverse Event
SAR	Serious Adverse Reaction
SAS	Safety Analysis Set
SIF	Safety Information sheet
UNL	Upper normal limit
UTN	Universal Trial Number

Protocol  
NN7088-4029  
UTN: U1111-1235-6007  
EU PAS No.

~~CONFIDENTIAL~~

Date:  
Version:  
Status:  
Page:

17 April 2020 | **Novo Nordisk**  
2.0  
Final  
10 of 49

WHO

World Health Organisation

Protocol  
NN7088-4029  
UTN: U1111-1235-6007  
EU PAS No.

~~CONFIDENTIAL~~

Date: 17 April 2020  
Version: 2.0  
Status: Final  
Page: 11 of 49

**Novo Nordisk**

### 3 Responsible parties

In this document physician refers to the individual overall responsible for the conduct of the non-interventional study at a study site.

The physician is accountable for the conduct of the study. If any tasks are delegated, the physician should maintain a list of appropriately qualified persons to whom he/she has delegated specified significant study-related duties. During any period of unavailability, the physician should delegate responsibility for study activities of patients to a specific qualified physician who should be readily available to patients during that time. If the physician is no longer able to fulfil the role of physician (e.g. if he/she retires), a new physician must be appointed in consultation with Novo Nordisk. The physician and site personnel must have sufficient English skills according to their assigned task(s).

The physician must follow the instructions from Novo Nordisk when processing data. The physician must take all necessary technical and organisational safety measures to prevent accidental or wrongful destruction, loss or deterioration of data. The physician must prevent any unauthorised access to data or any other processing of data against applicable law. Upon request from Novo Nordisk, the physician must provide Novo Nordisk with the necessary information to enable Novo Nordisk to ensure that technical and organisational safety measures have been taken.

Please refer to the Stand-alone documents ([Annex 1](#)) for additional information about responsible parties. A list of all collaborating institutions and physicians will be made available to authorities upon request.

### 4 Abstract

#### 4.1 Title

A multinational, prospective, open labelled, non-controlled, non-interventional post-authorisation study (PASS) of turoctocog alfa pegol (N8-GP) during long-term routine prophylaxis and treatment of bleeding episodes in patients with haemophilia. Version 2.0 draft 23 January 2020. Author

#### 4.2 Rationale and background

Novo Nordisk has developed turoctocog alfa pegol (N8-GP), a 40 kDa glycoPEGylated (PEG) human recombinant factor VIII (rFVIII) with an extended half-life, for the treatment and prophylaxis of haemophilia A.

Marketing authorisation applications for Esperoct® (N8-GP) have been submitted globally. Esperoct® was approved in the US in February 2019 followed by EU in June 2019.

As per guideline, it is a request from the European Medicines Agency (EMA) to collect additional clinical safety data and to ensure consistency between the outcome from the pre-authorisation

Protocol  
 NN7088-4029  
 UTN: U1111-1235-6007  
 EU PAS No.

~~CONFIDENTIAL~~

Date: 17 April 2020  
 Version: 2.0  
 Status: Final  
 Page: 12 of 49

**Novo Nordisk**

clinical trials and those from post-approval local clinical practice use of commercially available product.

The general safety profile of N8-GP for the treatment of patients with haemophilia A is well examined in long-term exposure data from the pivotal-phase 3 trial in adolescents and adults, in the paediatric phase 3 trial and the surgery phase 3 trial and is similar to the safety profile of currently approved FVIII products.

Specific pharmacological risks for FVIII replacement products include FVIII inhibitor development and allergic-type hypersensitivity reactions, which were evaluated in all phase 3 trials.

### 4.3 Research question and objectives

The research question behind the study is to gain additional knowledge on safety in prophylaxis patients and obtain additional clinical data on the use of N8-GP in the setting of local clinical practice.

The primary objective of the study is to investigate the safety of N8-GP including the PEG moiety during prophylaxis and long-term use in patients with haemophilia A as prescribed by the physician.

Secondary objectives are to further evaluate the general safety of N8-GP during routine prophylaxis (including FVIII inhibitors and allergic/hypersensitivity reactions) and long-term use in patients with haemophilia A as prescribed by the physician.

Exploratory objectives are to monitor possible clinical effects of long-term exposure to N8-GP prophylaxis in patients with haemophilia A, including assessments of kidney and liver function parameters, neurological function and patients' PEG plasma level.

The primary endpoint of the study is:

- Number of Adverse Events (AEs) reported during the study period

The secondary endpoint is:

- Number of Serious Adverse Events (SAEs) reported during the study period

The exploratory endpoints are:

- Number of AEs related to hepatic or renal function during the study period
- Number of AEs that are defined within the system organ classes "Nervous system" or significant deviations from expected neurologic function during the study period
- Changes in laboratory parameters during the study period; including the hepatic and renal function parameters
- Changes in PEG-plasma levels from study start to end of study
- Number of FVIII treatment requiring bleeding episodes reported during the study period

Protocol  
NN7088-4029  
UTN: U1111-1235-6007  
EU PAS No.

~~CONFIDENTIAL~~

Date: 17 April 2020  
Version: 2.0  
Status: Final  
Page: 13 of 49

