## 7 Rationale and background

Novo Nordisk has developed turoctocog alfa pegol (also referred to as N8-GP), a 40-kDa glycoPEGylated human recombinant coagulation Factor VIII (rFVIII) with an extended half-life, for the prophylaxis and treatment of bleeding episodes in patients with haemophilia A. N8-GP has improved pharmacokinetic (PK) properties including a 1.6 fold increase in terminal half-life compared with standard FVIII products, which offers the possibility of achieving FVIII levels in the range of moderate haemophilia A with a less burdensome every fourth day or twice weekly treatment regimen.

Marketing authorisation applications for Esperoct® have been submitted globally. Esperoct® was approved in the US in February 2019 followed by EU in June 2019, and Canada and Switzerland in July.

The regulatory approval of N8-GP was based on the comprehensive pathfinder™ programme, a phase 1 to 3a clinical programme including 270 unique previously-treated patients (PTPs) children,

Protocol  
NN7088-4029  
UTN: U1111-1235-6007  
EU PAS No.

~~CONFIDENTIAL~~

Date: 17 April 2020  
Version: 2.0  
Status: Final  
Page: 16 of 49

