**Novo Nordisk**

adolescents and adults with severe haemophilia A (FVIII activity  $\leq 1\%$ ). The phase 3 trials documented that N8-GP is efficacious for prophylaxis and treatment of bleeding episodes across all age groups and in providing effective haemostasis during and after major surgical procedures. The median annualized bleeding rate for adolescents and adults was 1.18 and for children 1.95. In children, 82 % of their target joints did not bleed during the main phase of the trial, and children overall also showed an enhanced quality of life. The overall success rate for the first treatment of a bleeding episode evaluated within 8 hours was 88 %.

The general safety profile of N8-GP for the treatment of patients with haemophilia A is well examined through the clinical development programme, where N8-GP was well tolerated and has demonstrated a safety profile in the pivotal phase 3 trial in adolescents and adults, in the paediatric phase 3 trial and the surgery phase 3 trial similar to that of currently approved FVIII products.

The Committee for Medicinal Product for Human use (CHMP) has raised a theoretical concern regarding potential long-term effects of PEG accumulation in organs and other tissues. Based on modelling data and supported by analyses of PEG plasma levels in clinical samples from adolescent/adult and paediatric patients participating in the N8-GP phase 3 trials, plasma steady-state PEG concentrations have been reached in the clinical trial programme without any indication of PEG-related adverse effects to date. The clinical safety of long-term exposure to N8-GP – including evaluation of potential clinical consequences of exposure to 40 kDa PEG in organs and tissues – is yet to be established.

As per guideline, it is a request from the European Medicines Agency (EMA) to collect additional clinical data and to ensure consistency between the outcome from the pre-authorisation clinical trials and those from post-approval local clinical practice use of commercially available product. Therefore, a post-marketing investigation should be performed. Novo Nordisk has received an obligation to conduct a Post-Authorisation Safety Study (PASS) to investigate the potential effects of PEG accumulation in organs and other tissues.

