**Novo Nordisk**

deviations from expected neurologic function during the study period

Changes in laboratory parameters during the study period, including hepatic and renal function parameters	From inclusion of the patient until end of study visit	Count of events
---	--	-----------------

PEG-plasma levels	At entry, after 2 years, and at the end of study	ng/mL
-------------------	--	-------

Number of FVIII treatment requiring bleeding episodes reported during the study period	As described in section 9.2.7.1	Count of events
--	---	-----------------

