**Novo Nordisk**

#### **9.2.7.4 PEG plasma level**

PEG plasma levels should be determined three times during the course of the study. This should preferably be done at baseline (visit 1), after two years of participation in the study and at the 'End of study visit'. Additionally, the responsible physician can request additional analyses if considered clinically warranted. The sample will be analysed at a special laboratory, contracted by sponsor, to determine the concentration of PEG in the patients' blood.

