#### **9.2.8.9 Dosing regimen**

The N8-GP dosing regimen at study entry and any changes in regimen during the study, must be recorded in the eCRF, including dosing regimen and date.

The physician should at each visit discuss the haemophilia treatment with the patient. The patient should be asked if the prophylaxis doses of N8-GP were taken as prescribed since last visit, and any deviations from the prescription must be recorded in the eCRF.

The physician should ensure that the patient notes down any treatment relevant details between the visits in his own personal notes/diary. The patient diary (for example national mobile application or personal paper diaries) must be used as a basis in the discussion during the routine visits to the clinic.

Protocol  
NN7088-4029  
UTN: U1111-1235-6007  
EU PAS No.

~~CONFIDENTIAL~~

Date: 17 April 2020  
Version: 2.0  
Status: Final  
Page: 28 of 49

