**Novo Nordisk**

Number of these specific AEs during study period will be summarised together with the number of patients with any of these AEs. Furthermore, listings will be provided displaying all these specific AEs.

- Changes in laboratory parameters during the study period, including hepatic and renal function parameters.

Laboratory parameters will be summarised by visit. Furthermore, change from baseline (visit 1) will be summarised. Listings and individual over time profile plots (where deemed relevant) will be provided displaying laboratory parameters reported during the study period.

- PEG-plasma levels at study entry, after two years and at the end of study

PEG plasma level will be summarised by visit. Listings and individual over time profile plots will be provided displaying PEG plasma level reported during the study period.

- Number of FVIII treatment requiring bleeding episodes reported during the study period

Number of FVIII treatment requiring bleeding episodes reported during the study period will be summarised. Furthermore, listings will be provided displaying all FVIII requiring bleeding episodes.

Definition of a bleeding episode: Multiple bleeding locations occurring during the same event (e.g., due to a bicycle accident) or at the same time point will be counted as one bleeding episode. A bleeding which occurs within 72 hours after stopping treatment of a previous bleeding event at the same or a subset of the same anatomical location(s) is considered a re-bleed, and is not a new bleeding episode. If a bleeding event occurs in the same location later than 72 hours after stopping treatment of a previous bleeding event it is considered a new bleeding episode.

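### The PEG plasma endpoint is worded two ways, and its pooled raw summary cannot by itself separate continued accumulation from initial rise, regimen change or washout

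*Protocol*

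**What the plan says.** The abstract (Protocol 4.3) lists the exploratory PEG endpoint as "Changes in PEG-plasma levels from study start to end of study". The endpoint table in 9.1.3 lists it as a level in ng/mL, with the time frame "At entry, after 2 years, and at the end of study". Section 9.2.7.4 matches the table: "PEG plasma levels should be determined three times during the course of the study", with further samples if the physician sees a clinical reason.

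For the analysis, 9.7.2.3 states "PEG plasma level will be summarised by visit" and adds "Listings and individual over time profile plots will be provided displaying PEG plasma level reported during the study period". The same section plans change from baseline for the laboratory parameters, but not for PEG. The firm subgroups in 9.7.2 are age and disease severity; patients with earlier inhibitors may be shown separately.

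Four design features bear on how a PEG level can be read:
- Patients who have already used N8-GP may enrol alongside new users (4.4).
- Treatment is left to the treating physician (9.1.4), and "any changes in regimen during the study, must be recorded in the eCRF" (9.2.8.9).
- Patients who stop N8-GP are ideally followed to the end of the study (9.1), and the analysis set keeps everyone exposed during the study (9.7.1).
- On earlier trials, section 7 says that "plasma steady-state PEG concentrations have been reached in the clinical trial programme".

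**The concern.** Section 7 explains that the study exists because a regulator raised a theoretical concern about PEG accumulating in organs and tissues. Plasma PEG is the only direct PEG measurement in the study, and 9.1 says it was requested by EMA. It is exploratory in rank but close to the question that prompted the study.

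A raw concentration averaged over all patients at a visit can move for reasons other than continued accumulation. A new user rises from no drug towards a plateau. A patient whose regimen changes moves to a different plateau. A patient who has stopped washes out. Followed as written, the summary pools all of these. A rise could reflect the share of new starters, and a flat or falling mean could hide a real upward drift. The two wordings add to the difficulty, because it is unclear whether the result to be reported is a start-to-end change or a set of levels.

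**Working it through.** The protocol states no PEG result, half-life, time to plateau, switching rate or share of new users, so there is no figure of its own to reproduce. The steps below show what the stated summary can and cannot separate. Every assumed value is marked.

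**1. Regimen change.** Section 7 refers to a "less burdensome every fourth day or twice weekly treatment regimen".
- Every fourth day: 7/4 = 1.75 infusions per week. Twice weekly: 2.
- Ratios at equal dose per infusion: 2/1.75 = 1.143 (+14%) and 1.75/2 = 0.875 (-12.5%).
- If the plateau is proportional to weekly load (assumed), raw ng/mL shifts by the same factor with no change in elimination.
- Illustration: suppose a share s moves from twice weekly to every fourth day and the true dose-adjusted ratio is r. The expected mean ratio is r × ((1 - s) + 0.875 × s).
  - s = 0.5, r = 1.10: 1.10 × 0.9375 = 1.031. A true 10% rise appears as 3%.
  - s = 0.5, r = 1.00: 0.938. No change appears as a 6% fall.
  - s = 1, r = 1.10: 1.10 × 0.875 = 0.963. A true 10% rise appears as a 4% fall.

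**2. Mixed entry.** Assume linear one-compartment build-up: level/plateau = 1 - 2^(-t/h), with t in months and half-life h. Suppose a share p enters with no PEG, the rest enter at plateau, and doses stay constant. The mean entry-to-end change, as a share of plateau, is p × (1 - 2^(-60/h)). With h = 3 months (assumed) and the end sample at 60 months, this is practically p. For p of 0, 25, 50, 75 and 100%, the mean change is 0, 25, 50, 75 and 100% of plateau. It reflects who enrolled.

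**3. How much the year-2 sample helps.** For a new user under the same model:

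| Assumed half-life (months) | Level at month 24 (% of plateau) | Further rise to month 60 (% of plateau) | Month-60 / month-24 ratio |
|---|---|---|---|
| 1 | 100 | 0 | 1.00 |
| 3 | 99.6 | 0.4 | 1.00 |
| 6 | 93.8 | 6.2 | 1.07 |
| 12 | 75 | 21.9 | 0.969/0.75 = 1.29 |
| 24 | 50 | 32.3 | 0.823/0.50 = 1.65 |

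Up to a half-life of about 6 months, year 2 to end is largely free of the initial rise. Beyond that it is not.

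**4. Washout.** The share of the level left 12 months after stopping is 2^(-12/h): about 0, 6, 25, 50 and 71% for half-lives of 1, 3, 6, 12 and 24 months. One off-drug end sample can therefore pull the visit mean down substantially.

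**5. Data available for a remedy.** Regimen at entry, dated changes and deviations from prescription are recorded (9.2.8.9). Consumption is built from regimen plus reported bleeds (9.3). Weighing is recommended, not required (9.2.8.10). Treatment history covers the regimen in the 12 months before entry, but requires the product name only when an inhibitor emerges (9.2.8.3). Earlier N8-GP use may therefore have to be inferred from the entry PEG level in some patients.

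**The case against.** The strongest defence is that the body of the protocol, not the abstract, governs the analysis. The body plans levels at three times with listings and a profile plot for each patient. A new user's low first point would be visible, and the year-2 sample helps to separate the early rise from later drift. This stands, and it limits the point. What remains is that the plots as described carry no dose and no on/off-drug marker, so a movement in a profile cannot be attributed from the plot alone.

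A second defence is that a dose-adjusted variable is ordinary material for a statistical analysis plan, which 9.7 allows for. This stands in part: no finding is made that detail is missing. The point is that the analysis the protocol does state pools unlike samples, while data already collected would support a better one. The two wordings also conflict within the protocol itself.

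A third is that plasma concentration is a legitimate description of exposure. It is, and the raw values should stay.

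A reader might infer more: that regimen changes and the rise to steady state will determine the PEG result in place of accumulation, or that the study has no link to dose at all. The documents support neither. They give no half-life, switching rate or share of new users, so how far these factors would move the result is unknown. Section 7 names the two regimens as alternatives and says nothing about patients switching between them. The link to dose is absent from the stated analysis, not from the data. Nor is the start-to-end contrast wrong for everyone: for patients already at plateau on entry it is the longest informative comparison.

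**Conclusion.** The point holds in limited form. The PEG endpoint is stated inconsistently between 4.3 and 9.1.3/9.7.2.3. The pooled raw summary can confound continued accumulation with initial rise, regimen change or washout, and the year-2 sample and individual plots resolve this only partly.

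The only size that rests on the protocol's own figures is the 12.5-14% shift between the two named regimens, and it still assumes equal dose per infusion and a plateau proportional to weekly load. The mixed-entry and washout effects could be larger, but they depend on an assumed half-life and, for mixed entry, on an unknown share of new users. The 10% drift and the switching shares in the working are illustrations, not predictions.

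The endpoint is exploratory and descriptive with no hypothesis test, and study size was set by regulatory request (9.5). The correction is worth making because it is cheap and concerns the study's only direct PEG measurement.

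**What to change.** Reconcile 4.3 with 9.1.3 and 9.7.2.3 so that the PEG endpoint has one definition. In 9.7.2.3 keep the raw ng/mL summaries, listings and plots, and add:

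1. PEG level relative to recorded N8-GP consumption before the sample, using the dated regimen, deviations from prescription and treatment of bleeds, and per kg where a weight is available. Prescribed dose alone would leave out bleed treatment and missed doses.
2. Summaries that separate on-drug from off-drug samples, and patients new to N8-GP at entry from those already using it. Classify prior use from treatment history or, where the product is not recorded, from the entry PEG level.
3. A within-patient ratio, end of study to year 2, of the dose-normalised level in patients still on N8-GP, as a supportive accumulation contrast. Keep entry-to-end for patients already on long-term N8-GP at entry. State that a plateau by year 2 is an assumption.

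The cost is wording in these sections and a few derived variables, with no new samples or visits. The downside is that the added contrasts use only patients with both samples and usable dose data, and the per-kg version will be missing where weight was not taken.
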